11.5 Handling of Data

All study three sites will enter study data into a password protected, secure RedCap database that will be managed by the DFCI study team. Data will be stored for the duration of the study enrollment and analysis period and will be deleted once study analysis/write-up is complete. Hard copies of the questionnaires will be kept in a locked filing cabinet and destroyed upon study completion.

12.0 Provisions to Monitor the Data to Ensure the Safety of Subjects

12.1 NA

13.0 Withdrawal of Subjects

- 13.1** Subjects may be withdrawn without consent if their treating provider feels they should no longer participate in the study.
- 13.2** In the event of orderly termination, subjects will be notified that they will no longer be enrolled in the study. Study PIs will be made available to discuss any of the subjects' questions or concerns.
- 13.3** If a subject wishes to withdraw fully from the study, the study team will cease all data collection relating to the withdrawn subject, including review of primary outcomes. If a subject wishes to forgo the completion of the post-transfusion QUALMS or two-month follow-up questionnaire, the study team will confirm with the participant whether it is permissible to continue collecting data regarding the patient's health outcomes/healthcare utilization, as relevant to the study.

14.0 Risks to Subjects

14.1 As this is a survey study, we do not anticipate any risks due to study participation. The only foreseeable risk is potential emotional distress due to the nature of the questionnaires. If a participant becomes upset at any point, he/she will be referred to appropriate resources (e.g., social work, counseling). In the unlikely event that a patient is made upset or uncomfortable by the QUALMS survey, the study investigators will contact the treating physician to inform him or her of the patient's concerns.

14.2 *NA*

14.3 *NA*

14.4 *NA*

15.0 Potential Benefits to Subjects

15.1 Potential Benefits

It is possible that this research study may benefit participants directly if subjects and/or their physician take the results of the PTQA report into consideration when making transfusion decisions. It is our goal that providing patients/providers with an accurate assessment of pre- and post-transfusion QOL will facilitate a better-informed discussion regarding transfusion.

15.2 Other

PROTOCOL TITLE: A New Paradigm of Transfusion Decision Support for Patients with MDS: Using Peri-Transfusion Quality of Life Assessments (PTQAs)

If participants and/or providers elect not to use the results of the PTQA report to guide transfusion decisions, then this study will not benefit participants directly.

16.0 Vulnerable Populations

16.1 NA

17.0 Community-Based Participatory Research

17.1 NA

18.0 Sharing of Results with Subjects

18.1 Study participants and their providers will receive the results of the PTQA. Once the participant has completed the post-transfusion QOL assessment, the RA will generate a report that compares the participant's pre- and post-transfusion QOL scores. This information will be compiled in a PTQA report and shared with the provider and patient via email.

19.0 Setting

19.1 Once a potentially eligible subject is identified and upon provider approval, the RA will meet the patient in clinic to initiate the consent discussion. After a patient consents to the study, he/she will be given a copy of the QUALMS and instructed to complete the survey at home on the day before the upcoming transfusion. The RA will meet the participant in clinic when he/she comes in for a scheduled transfusion. At this appointment, the RA will collect the completed pre-transfusion survey and will give the participant a second copy of the QUALMS to take home. The participant will be instructed to complete the survey at home one week post transfusion and return it by mail. Study participants will also receive the follow-up questionnaire by mail to be completed at home.

20.2 Other Resources

The three study sites—DFCI, YCC, and WFB—all have large MDS populations and demonstrated track records in high-impact research in MDS, QOL, geriatrics and hematologic malignancies.

21.0 Prior Approvals

21.1 We have obtained multi-center approval. No other approval is necessary for this study.

22.0 Recruitment Methods

22.1 Recruitment Procedure

Once the RA has identified potential study participants and confirmed eligibility with the patients' provider, potential study participants will be informed of the study at the appointment prior to their first/next transfusion.

- Patients that are nearing first transfusion will be approached at the appointment prior to their first transfusion.
- Patients that are transfusion-dependent will be approached at an upcoming appointment or transfusion.

Study consent will take place during these visits. Potential participants will be given the opportunity to ask questions, opt out of consideration, and take a consent form home to discuss further with their family and/or other clinicians. We will be clear that enrollment does not mean patients are required to forgo future transfusion if the resulting PTQA report indicates an unimproved or worsened QOL post-transfusion.

Once consented, all DF/HCC study participants will be registered in the DFCI OnCore Clinical Trial Management System by the RA as required by DF/HCC SOP REGIST-101.

- 22.2** The source population for this study is patients with MDS that are presenting to clinic for treatment with blood transfusion.
- 22.3** Eligible subjects will be identified using our study-specific Epic Workbench Report (as described above).

22.4 NA

22.5 NA

23.0 Local Number of Subjects

- 23.1** The target accrual at DFCI will be dependent upon accrual at external sites. subjects.
- 23.2** We will approach 90 participants across all three sites with a goal of enrolling 60 total evaluable participants study-wide. In addition to these 60 evaluable participants, we will have 60 historical controls that will be matched based on transfusion group.

24.0 Provisions to Protect the Privacy Interests of Subjects

- 24.1** During the consent process, the consenting member of the study team will communicate clearly that participants should feel no obligation to share more information than they are comfortable with. It will be made clear that participants can opt out of any question(s) on the questionnaire that may cause uneasiness.

**PROTOCOL TITLE: A New Paradigm of Transfusion Decision Support for Patients with MDS:
Using Peri-Transfusion Quality of Life Assessments (PTQAs)**

24.2 The study team will be trained to respond to participant questions and inquiries with compassion and professionalism. Again, participants will be informed that they can skip any questions that cause discomfort.

24.3 The research team will only have access to information that is relevant to the study, including in participants' medical records. The team will follow HIPAA guidelines regarding patient information.

25.0 Compensation for Research-Related Injury

25.1 NA

25.2 NA

26.0 Economic Burden to Subjects

26.1 NA. There are no costs that subjects may be responsible for because of participation in the research.

27.0 Consent Process

27.1 We will be obtaining written consent for this study per SOP: Informed Consent Process (CON-100). Once a potentially eligible subject is identified, the RA will approach the subject at an upcoming appointment. The RA will book a consult room on the clinic floor to discuss the study with the subject either before or after an appointment with a provider. If the subject is interested, but not prepared to sign consent on the day of discussion, he/she can opt to sign up for the study at a later date.

28.0 Process to Document Consent in Writing

28.1 To obtain written consent, we will follow the DFCI SOP for the Informed Consent Process (CON-100).

28.2 NA. We will not be requesting a waiver of the requirement to obtain written documentation of consent.

28.3 We have submitted an Informed Consent Form for review alongside this protocol.

Using Peri-Transfusion Quality of Life Assessments (PTQAs)

APPENDIX A: Survey Cover Page

A New Paradigm of Transfusion Decision Support for Patients with MDS

Pre-Transfusion Questionnaire

Instructions:

Please complete this survey at home on the day before your next transfusion
and bring it with you to your appointment.

Initials: _____

Study ID: _____

Date survey complete: _____

How would you like to receive your quality of life report? Mail Email
 In person

If by email, what is your email address? _____

APPENDIX B: THE QUALMS

Initials: _____

Study ID: _____

Date: _____

Pre or Post Transfusion: _____

The QUALMS

rights reserved.

The Quality of Life in Myelodysplasia Scale

Copyright © 2013 Dana-Farber Cancer Institute, Inc. and CHEO Research Institute, Inc. All

Patients often have different experiences over the course of their illness; however, please limit your responses to your experience **over the past week only**. The information you provide will remain strictly confidential.

During the past week, how often...		Never	Rarely	Sometimes	Often	Always
1	...did you feel as though there was a lack of clear information about your disease?					
2	...have you felt there was limited emotional support available for patients with MDS beyond their families?					
3	...did you feel as though you couldn't do anything about your disease?					
4	...did you feel the course of your disease was unpredictable?					
5	...did you have difficulty explaining MDS to your friends or family?					
6	...did you have trouble concentrating?					
7	...have you considered changing long-term plans due to health concerns?					
8	...have you experienced shortness of breath?					
9	...did low energy levels cause you to change your schedule?					
10	...did you feel as though your life was organized around medical appointments?					
11	...have you felt a sense of hopelessness?					
12	...have you been worried about getting an infection?					
13	...have you had sufficient energy for routine tasks?					
14	...were you afraid of dying?					
15	...did you feel angry about your diagnosis?					

PROTOCOL TITLE: A New Paradigm of Transfusion Decision Support for Patients with MDS:
Using Peri-Transfusion Quality of Life Assessments (PTQAs)

16	...were you worried about bleeding?					
17	...did you feel a sense of gratitude for a part of life that you took for granted before?					
18	...did you feel nauseated?					
19	...did you worry about your MDS progressing or developing into leukemia?					
20	...did you take into account that you might be fatigued when planning your activities?					

For the following questions, please again mark the answer choice that best represents your experiences and feelings over the past week. The information you provide will remain strictly confidential.

During the past week, how often...		Never	Rarely	Sometimes	Often	Always
21	...were you concerned that your MDS caused a financial burden for you or your family?					
22	...did you feel your family relationships were strained by your disease?					
23	...have you felt weak?					
24	...have you been too tired to take on the responsibilities you used to have?					
25	...did you worry about becoming a burden to your friends or family?					
26	...were you unable to participate in activities you are used to doing?					
27	...have you felt anxious about test or lab results?					
28	...did you avoid crowds because of fear of getting an infection?					
29	...did you find yourself grateful for tomorrow?					
30	...did you feel you were able to find quality information about MDS treatments?					
31	...were you concerned about bruising?					
32	...did you feel as though there were a lack of concrete answers about what will happen with your MDS?					
33	...did you experience a change in bowel habits?					

PROTOCOL TITLE: A New Paradigm of Transfusion Decision Support for Patients with MDS:
 Using Peri-Transfusion Quality of Life Assessments (PTQAs)
 For the following questions, **you may select “not applicable”** if the question does not apply to you.

During the past week, how often...		Never	Rarely	Sometimes	Often	Always
34	...were you afraid of losing your job? (check here if not applicable because you are unemployed/retired)					
35	...did you feel too tired to drive? (check here if not applicable because you do not drive)					
36	...were you afraid to have sex due to your blood counts? (check here if not applicable because you are not currently sexually active)					
37	...were you afraid that your MDS treatment would stop working? (check here if not applicable because you are not currently being treated)					
38	...have you been too tired to take care of a family member or loved one? (check here if not applicable because you are not providing such care)					

[figure not shown]

PROTOCOL TITLE: A New Paradigm of Transfusion Decision Support for Patients with MDS:
Using Peri-Transfusion Quality of Life Assessments (PTQAs)

APPENDIX C: PTQA Reports

PTQA Score Report (UNCHANGED SCORE)

Thank you for participating in the Peri-Transfusion Quality of Life Assessment (PTQA) study. The goal of this study is to determine whether the use of a quality of life questionnaire can help patients with MDS and their providers make better informed transfusion decisions. We hope that you will use the information in this PTQA score report to discuss future transfusion options with [Provider name].

What does your score mean?

Since your first and second scores are within 5 points of each other, your quality of life has **remained stable** after transfusion.

How should you use the score?

Given that your quality of life did not improve after your transfusion, we recommend that you discuss the benefits and risks of transfusion with your doctor.

Based on a focus group we conducted as part of our research, experts on myelodysplastic syndromes (MDS) agree that it is safe for patients with MDS to increase the time between transfusions or stop them altogether, as long as they are otherwise healthy, experience no significant benefit in their quality of life, and their hemoglobin level stays above 7.5 g/dL.

Your PTQA score suggests that you might consider limiting the number of transfusions you receive. However, there may be other explanations for your quality of life score. We encourage you to use this report to discuss future transfusion decisions with your doctor.

What are the next steps in the study?

The study team will contact you to complete your follow-up survey during the week of [date].

Questions or comments?

[figure not shown]
Please contact the [study team - provide site-specific study contact].

PROTOCOL TITLE: A New Paradigm of Transfusion Decision Support for Patients with MDS:
Using Peri-Transfusion Quality of Life Assessments (PTQAs)

PTQA Score Report (DECREASE)

Thank you for participating in the Peri-Transfusion Quality of Life Assessment (PTQA) study. The goal of this study is to determine whether the use of quality of life assessments can help patients with MDS and their providers make better informed transfusion decisions. We hope that you will use the information in this PTQA score report to discuss future transfusion options with [Provider name].

What does your score mean?

Since your second score is more than 5 points lower than your first, you have experienced a clinically significant **decrease** in your quality of life after transfusion.

How should you use the score?

Given that your quality of life did not improve after your transfusion, we recommend that you discuss the benefits and risks of transfusion with your doctor.

Based on a focus group we conducted as part of our research, experts on myelodysplastic syndromes (MDS) agree that it is safe for patients with MDS to increase the time between transfusions or stop them altogether, as long as they are otherwise healthy, experience no significant benefit in their quality of life, and their hemoglobin level stays above 7.5 g/dL.

Your PTQA score suggests that you should consider limiting the number of transfusions you receive. However, there may be other explanations for this change in your quality of life score. We encourage you to use this report to discuss future transfusion decisions with your doctor.

What are the next steps in the study?

The study team will contact you to complete your follow-up survey during the week of [date].

Questions or comments?

[figure not shown]
Please contact the [study team - provide site-specific study contact].

PROTOCOL TITLE: A New Paradigm of Transfusion Decision Support for Patients with MDS:
Using Peri-Transfusion Quality of Life Assessments (PTQAs)

PTQA Score Report (INCREASE SCORE)

Thank you for participating in the Peri-Transfusion Quality of Life Assessment (PTQA) study. The goal of this study is to determine whether the use of quality of life assessments can help patients with MDS and their providers make better informed transfusion decisions. We hope that you will use the information in this PTQA score report to discuss future transfusion options with [Provider name].

What does your score mean?

Since your second score is more than 5 points higher than your first, you have experienced a clinically significant **increase** in your quality of life after transfusion.

How should you use the score?

Given that your score indicates a clinically significant increase in your quality of life, we do not recommend that you change your transfusion plan at this time. We encourage you and your provider to take changes in your quality of life into consideration when making transfusion decisions in the future.

What are the next steps in the study?

The study team will contact you to complete your follow-up survey during the week of [date].

Questions or comments?

Please contact the [study team - provide site-specific study contact].

PROTOCOL TITLE: A New Paradigm of Transfusion Decision Support for Patients with MDS:
Using Peri-Transfusion Quality of Life Assessments (PTQAs)

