Per Protocol 18-604, we convened an expert panel of 13 MDS physicians (12 MDS experts; 1 blood bank physician) at the national AAMDSIF Symposium to determine the minimum safe Hb level. All panel participants received a literature review and questionnaire via email prior to the in-person panel. This questionnaire comprised round one of the modified Delphi. Among several critical questions (see Protocol 18-604), we asked: *“Please mark the lowest hemoglobin at which you think it would be safe to forgo transfusions for patients with MDS given no evidence of end-organ damage.”* Once we received participants’ responses, we tabulated them and provided a summary of the results to the experts at our in-person panel. We allowed time for open discussion of each question. Following this discussion, we asked participants to fill out a round two questionnaire, the results of which were compiled and disseminated via email. We then asked the expert panel to fill out a third round of questions via email. While we were unable to reach a consensus threshold of 75% after three rounds, **we did have 100% consensus that the minimum safe Hb level should be no less than 7.5 g/dL.**

Accordingly, we will use this threshold to identify eligible patients for our study, meaning patients with an Hb level less than 7.5 g/dL will be ineligible for participation.

Epic Workbench Report

To systematically identify patients who would benefit from PTQA, a member of our study team, [name] (Medical Director for Clinical Information Systems at DFCI), is currently working with DFCI’s Epic team to create a Workbench report. This report will identify patients with MDS that are facing transfusion decisions. Epic is an EHR that covers 190 million patients in the U.S., including at the three centers participating in this project. Since May 2015, Epic has been the enterprise EHR for DFCI/BWH. It was previously adopted by Yale Cancer Center (YCC; 2013) and Wake Forest Baptist (WFB; 2012), the other two pilot sites.

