3.2 Inclusion/Exclusion Criteria

Inclusion criteria:

1. Age \geq 18 years of age
2. Patients with MDS, including t-MDS and MDS/MPN
3. Transfusion-naive group: approaching Hb of 8.5 g/dL during enrollment period
 - a. Ideally never-transfused (have never received red cell transfusion)
 - b. If not never-transfused, participants are also eligible for inclusion in this group if they have not been transfused with red cells within last 8 weeks
4. Transfusion-dependent group: Patients with \geq 1 transfusion scheduled during 8-week period prior to enrollment
5. Ability to read and understand English

Exclusion criteria:

1. Age $<$ 18 years
2. Cr $>$ 2
3. Known CHF
4. Unstable Angina
5. Hb level below 7.5 g/dL
6. No plans for potential future outpatient transfusion.

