We may find that patients and hematologists do not use the information in their PTQA reports to truly affect decision-making, as both may be anxious to forgo transfusions despite the fact that QOL did not improve. We plan to assess this parameter at two months post-transfusion by asking participants whether they discussed the PTQA report with their physician (see Appendix B). To help prevent the PTQA going unused, we will make sure that providers at each site have access to the consensus Hb data from our previous qualitative study (Protocol 18-064). These results will be disseminated to providers prior to study initiation. In addition, we will work closely with the DFCI Adult Patient and Family Advisory Council (PFAC) to vet the routine language in our PTQA patient reports so that is optimally educational and anxiety-reducing.

PROTOCOL TITLE: A New Paradigm of Transfusion Decision Support for Patients with MDS: Using Peri-Transfusion Quality of Life Assessments (PTQAs)

Exploratory analyses (e.g. descriptive statistics such as means and standard deviations) using the results from the follow-up survey (see Appendix B) will characterize decisional regret, perceptions of care, and perceived stress by the associated scales at two months post-transfusion (Table).

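### Two of the three PTQA report templates claim more expert agreement on safety above Hb 7.5 g/dL than Protocol Section 2.2 shows, and the templates' score bands do not match Section 9.2 at exactly 5 points

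*Protocol*

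**What the plan says.** **Safety sentence.** In Appendix C, the unchanged and decrease templates both state that MDS experts "agree that it is safe for patients with MDS to increase the time between transfusions or stop them altogether", on the conditions "as long as they are otherwise healthy, experience no significant benefit in their quality of life, and their hemoglobin level stays above 7.5 g/dL". The increase template has no such sentence.

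**Evidence for it.** Section 2.2 describes a 13-member panel and three Delphi rounds. It quotes one question, which asked for the lowest Hb at which transfusion could safely be forgone when there is no end-organ damage. The team was "unable to reach a consensus threshold of 75% after three rounds", but reports "100% consensus that the minimum safe Hb level should be no less than 7.5 g/dL". The protocol uses this result to exclude patients with Hb below 7.5 g/dL.

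**Score bands.** Section 9.2 (item 9) and Appendix F call a change *within 5* points stable and a change of *5 or more* improved or declined. The Appendix C templates use *within 5* for unchanged and *more than 5* for increase and decrease.

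**The concern.** The report is what the intervention delivers, and the safety sentence is the reassurance behind its suggestion to limit transfusions. If the sentence goes beyond what the panel agreed, patients weigh that suggestion on a stronger assurance than the protocol can show. The topic is close to the study population: transfusion-naive participants enter when "approaching Hb of 8.5 g/dL during enrollment period" and are excluded below 7.5, so the safety of levels not far above 7.5 is a live question for them.

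The score bands decide which message a patient receives. At +5 the possible messages point in opposite directions: the increase report recommends no change of plan, while the unchanged report suggests that the patient might limit transfusions.

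**Working it through.** No power or sample-size figure is involved. The first check compares two statements, and the second classifies score changes.

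**1. Floor versus agreed safety**

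Let *m* be the Hb that a given panelist regards as the minimum safe level.

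- Section 2.2 reports that *m* ≥ 7.5 for every panelist.
- The template sentence needs every level above 7.5 to be safe in the experts' view, that is *m* ≤ 7.5 for those said to agree.

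A panelist with *m* = 8.0 or 8.5 satisfies the first statement and contradicts the second. The two coincide only if the panel settled on *m* = 7.5, and Section 2.2 reports no consensus on a level. The exclusion of patients below 7.5 is a correct use of the floor, because no panelist thought such levels safe. The template uses the converse, which does not follow.

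The conditions differ too. The quoted question specified no end-organ damage. The templates say *otherwise healthy* and add a QOL condition that the question did not contain. The provider email in Appendix D keeps the end-organ condition and claims no expert agreement, so the patient gets the stronger statement.

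**2. Bands at exactly 5 points**

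With *d* = post score minus pre score:

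| *d* | Reading of *within 5* | Section 9.2 and Appendix F | Appendix C template text |
|---|---|---|---|
| +4, 0, -4 | either | stable | unchanged |
| +6 | either | improved | increase |
| -6 | either | declined | decrease |
| +5 | 5 or less | stable and improved | unchanged |
| +5 | less than 5 | improved | none fits |
| -5 | 5 or less | stable and declined | unchanged |
| -5 | less than 5 | declined | none fits |

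On neither reading do the templates match Section 9.2 at ±5. At the other values they agree. At -5 the unchanged and decrease reports differ in the result stated (stable against a clinically significant decrease) and in the strength of the advice (*might* against *should* consider limiting).

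With stable defined as |*d*| < 5, improved as *d* ≥ 5 and declined as *d* ≤ -5 in all places, every value of *d* falls in exactly one band and one template. This fits Section 9.2's statement that a meaningful difference starts at 5 points.

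**The case against.** **The panel was asked more than is shown.** Section 2.2 says that the Hb question was one of several and refers to a separate protocol for the rest. The template sentence covers spacing, stopping and QOL benefit, none of which appears in the quoted question beyond forgoing transfusion, so it may rest on another item. This stands. A reader might infer that the sentence is false; the document shows only that it is unsupported here.

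**A reader might also try to count dissenters.** With 13 panelists, 0.75 × 13 = 9.75, so 10 were needed for consensus. At most 9 could then have chosen 7.5, leaving at least 4 of 13 (31%) above it. With 12 respondents, 9 were needed and again at least 4 (33%) remain. This assumes that the 75% rule applied to a single Hb level and that 12 or 13 panelists answered the last round. Section 2.2 states neither and gives no votes, so the count is not a finding.

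**Safeguards exist.** Section 11.1 has "providers at each site have access to the consensus Hb data from our previous qualitative study" and has the patient council vet report language. Section 22.1 makes clear that "enrollment does not mean patients are required to forgo future transfusion". The reports send patients to their doctor and allow for other explanations of the score. Section 3.2 excludes creatinine above 2, known CHF and unstable angina. These lower the risk, but the patient still reads the same sentence.

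**The Hb at the time of reading is unknown.** The values 8.5 and 7.5 apply at entry, and the report follows a transfusion by at least about a week. A reader might infer that recipients are then in the disputed range; the documents do not show it.

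**Section 9.2 can be read coherently.** *5 or more* implies that *within 5* means less than 5. Staff who apply Section 9.2 would then class +5 as improved and could send the increase report, with one inexact sentence in it. This largely stands. The wrong message at +5 is possible but not certain, and the necessary correction is mainly in the templates.

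**Conclusion.** The point holds as a minor, inexpensive correction in two parts.

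1. Two of the three templates tell patients that experts agree on safety above 7.5 g/dL, while the protocol shows only a unanimous lower bound and no consensus on a level. This conclusion assumes that no unshown panel item supplies the missing agreement.
2. The template text and Section 9.2 disagree at two values, +5 and -5. A patient whom Section 9.2 calls clinically improved could be told that QOL did not improve, and a clinically significant decline could be reported as stable.

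How many patients this touches cannot be worked out. The protocol gives no QUALMS scoring rule, standard deviation or expected change. The whole-number scores in Appendix D suggest, but do not prove, that an exact 5-point change can occur. A reader might take the point as a threat to the historical-control comparison. It is not: it concerns the content of the intervention, and the endpoint definitions, sample size and power statements are unaffected.

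**What to change.** **Safety sentence (unchanged and decrease templates).** Say that the experts agreed the minimum safe Hb is no lower than 7.5 g/dL but did not reach consensus on a specific safe level. State the panel's condition of no end-organ effects of anemia, as the Appendix D email already does. If another panel item does support the present wording, keep the wording and report that item and its result in Section 2.2.

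**Score bands.** In the increase and decrease templates, change *more than 5* to *5 or more*. In the unchanged template, change *within 5* to *less than 5*. Make the same *less than 5* clarification in Section 9.2 and Appendix F.

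**Cost.** One sentence in two templates, band wording in three templates and two protocol sections, and a routine amendment. No data collection or analysis changes.
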